9.4.1 Dose Interruptions

Dose interruptions for Grade 2 toxicity for up to 1 week can be implemented at the discretion of the treating physician to manage intolerable or clinically significant toxicity. No dose reduction is required when resuming treatment.

Dose interruptions in the middle of a treatment cycle will not affect the cycle and day count on the schedule of assessments. For example, if study drug(s) is (are) held on Cycle 1 Day 10, the following day should still be called Cycle 1 Day 11. If a dose interruption occurs at the

beginning of a new cycle, then the new cycle and day count will begin when study drug is restarted. For example, if study drug is held at the Cycle 2 Day 1 visit, then the day that the patient does resume dosing will be called Cycle 2 Day 1.

9.4.2 Holding of Study Drug

Study drug (PLX9486, PLX3397, and sunitinib) should be held at least 3 days prior to local radiation therapy either for pain palliation or to control slowly progressive disease. Study drug may be resumed 7 days after the completion of radiation therapy at the earliest provided that radiation related skin changes, if any, have resolved. Any AE related to radiation treatment that occurs up to and including 21 ± 7 days after administration of the last dose of study drug must be reported following instruction specified in [Section 13.2](#).

9.5 Concomitant Medications and Procedures

Concomitant treatment is permitted if the medication is not expected to interfere with the evaluation of safety or efficacy of the study drug. During the study, if the use of any concomitant treatment becomes necessary (e.g., for treatment of an AE), the treatment must be recorded on the eCRF, including the reason for treatment, generic name of the drug, dosage, route, and start and stop dates of administration.

Of the five major CYP isoforms, 3A4 may be involved in metabolism of PLX3397, with possibly CYP1A2 playing a minor role. PLX3397 is an inhibitor of CYP2C9, CYP2C19, and CYP3A4 in the range of 1 to 30 μ M. Until information regarding exposure toxicity and exposure-response relationships are available with PLX3397, concomitant CYP3A4 inhibitors and inducers should be administered with caution, in the event they alter the systemic exposure to PLX3397 (see [Attachment 2](#) for a list of common CYP3A4 inhibitors and inducers). PLX3397 is an inducer of CYP2C8 and 3A4. In general, strong inhibitors, substrates or inducers of CYP3A4 should be avoided unless absolutely clinically necessary. These include anticonvulsants, mycin antimicrobials, and antiretrovirals. Some common examples include inhibitors such as erythromycin, verapamil, itraconazole, and inducers such as rifampicin, carbamazepine, phenytoin, efavirenz, and nevirapine.

The in vitro analysis of PLX9486 indicates that the drug does not inhibit or induce any of the major CYP enzymes. CYP3A4 appears to be the main CYP enzyme that metabolizes PLX9486. CYP2C8, 2C19 and 2D6 play a minor role in metabolizing PLX9486. It is recommended to avoid concomitant CYP3A4 inhibitors and inducers with PLX9486.

Patients enrolled in studies with PLX3397 who are also receiving concomitant warfarin should have their anti-coagulation status carefully monitored, especially shortly after initiation of PLX3397, for the potential need to make adjustments in warfarin dosing. In particular, the international normalized ratio (INR) should be obtained just prior to initiation of PLX3397, within 1 to 2 weeks after initiation, and periodically thereafter. Dose adjustments of warfarin should be made as medically indicated.

Patients enrolled in Part 2b and ■ are discouraged from taking proton pump inhibitors (PPIs) or other strong anti-acids (e.g., H-2 antagonists), as these may interfere with the reliable identification of the MTD or R2PD for the PLX9486 and PLX3397 combination.

Patients with isolated or locally progressive metastatic disease amenable to local therapy (e.g., Surgery or chemoembolization for an isolated lesion) may continue on study therapy after their procedure if they are deriving clinical benefit in the judgment of the principal investigator. The patient should stop study drug(s) 3 days prior to the procedure and may resume study drug(s) 7 days after the procedure. The principal investigator should discuss the case with the medical monitor prior to the procedure, including any modification to these guidelines.

Please consult the package insert for other information on sunitinib.

9.6 Precautions and Restrictions

This is the first-in-human study for PLX9486; there are no non-medication-related restrictions or precautions for PLX9486.

Because PLX3397 is a substrate for CYP3A4/5 and grapefruit juice is a CYP3A4/5 inhibitor, foods or beverages containing grapefruit should be avoided throughout the study. Concomitant use of food and herbal preparations that are strong CYP3A4 inhibitors or inducers should be avoided while on study as both PLX9486 and PLX3397 are primarily metabolized by CYP3A4. See [Attachment 2](#) for a list of strong CYP3A4 inhibitors and inducers.

9.7 Management of Clinical Events

All necessary support care shall be available to patients. For dose-modification guidelines, see [Section 9.4](#).

9.8 Blinding and Unblinding

Blinding methods will not be employed; PLX9486, PLX3397, and sunitinib will be administered in open-label fashion.

9.9 Preparation, Reconstitution, and Dispensation

[figure not shown]
PLX9486, PLX3397, and sunitinib are anticancer drugs and, as with other potential toxic compounds, caution should be exercised when handling PLX9486, PLX3397, and sunitinib. Specific instructions on preparation, reconstitution, and dispensation will be provided in the PLX121-01 Pharmacy Manual.

9.10 Packaging and Labeling

PLX9486 tablets (50 mg strength) are manufactured, packaged and labeled according to GMP and GCP at the following facility:

PLX3397 capsules (200 mg strength) are manufactured, packaged, and labeled according to GMP and GCP at the following facility:

Sunitinib is commercially available. Please refer to the USPI for further information.

9.11 Storage, Handling, and Accountability

PLX9486 tablets and PLX3397 capsules will be stored at the clinical site, as indicated on the study drug label, i.e., room temperature, between 15–30°C (59–86°F). Subjects will be requested to store the study drug at the recommended storage conditions noted on the label, out of the reach of children or other cohabitants.

Sunitinib is commercially available. Please refer to the USPI for further information.

The study drug provided in accordance with this protocol will be kept in a secure place, and will only be supplied to subjects participating in this study. The principal investigator is accountable for all study drug supplied by the sponsor in accordance with this protocol. In addition, the principal investigator must keep accurate and up-to-date dispensation records. Any study drug accidentally or deliberately destroyed must be recorded in a timely fashion, including an explanation for the destruction in writing. Any discrepancies between the amounts of Study drug dispensed and returned must also be explained in writing. All such records of drug accountability must be entered on the corresponding Subject eCRF's.

Specific details and instructions on handling and destruction of unused and partially used study drug will be provided in the PLX121-01 Pharmacy Manual.

9.12 Other Protocol-Specified Materials

There are no other supplies or materials required by the protocol.

10.1.1 Study Committee

The Study Committee will consist of the Sponsor's Medical Monitor, Clinical Program Manager, and the Principle Investigators. The committee will review study data prior to dose escalation and advise on study conduct and protocol design. In addition, in the event of a subject death believed to be possibly or probably related to study drug, the committee will review the information and provide a recommendation regarding further enrollment.

10.2 Arrangements for Recruitment of Subjects

Recruitment and enrollment strategies for this study may include recruitment from the investigator's local practice or referrals from other physicians. If advertisements become part of the recruitment strategy, they will be reviewed by the institutional review board (IRB) and/or independent ethics committee (IEC).

10.3 Treatment Group Assignments

This is an open-label, sequential dose-escalation study with extension cohorts. The initial dose level of PLX9486 will be 250 mg/day. Thereafter, dose-escalation groups will occur as described in [Section 9.2.1](#). Extension cohorts will be enrolled in parallel at the RP2D according to inclusion and exclusion criteria ([Section 8.1](#) and [Section 8.2](#)). The initial dose of PLX3397 will be 600 mg/day administered BID. Thereafter, dose escalation groups will occur as described in [Section 9.2.1.2](#). For the combination cohort with sunitinib the initial sunitinib dose will be 25 mg/day. Further details may be found in [Section 9.2.1.2](#).

10.4 Withdrawal of Patients from Drug Treatment or from the Study and Patient Replacement

The Plexxikon Medical Monitor will monitor safety data throughout the course of the study. The Medical Monitor will review SAEs within timeframes mandated by company procedures and will review trends, laboratory data, and AEs at periodic intervals and provide for interim safety analyses if appropriate.

The reasons a patient may discontinue or be withdrawn from the study include, but are not limited to, adverse event, clinically significant disease progression, patient request, investigator decision, protocol violation, patient noncompliance, and study termination by the Sponsor or institutional review board (IRB)/independent ethics committee (IEC). When a patient discontinues or is withdrawn, the investigator will notify the Sponsor and should perform the procedures indicated in the End of Study column in the Schedule of Events within 30 days after discontinuation of study drug and before initiation of any new anti-cancer therapy. Follow-up information will be obtained for patients who discontinue their participation in or are withdrawn from the study.

Patients withdrawn from the study for reasons other than toxicity or clinically significant disease progression (e.g., protocol violation or noncompliance) may be replaced at the discretion of the medical monitor and the investigator. Study drug administration may be discontinued due to an adverse event or at the discretion of the investigator.

The consequence of withdrawal of consent by a patient will be that no new information will be collected from that patient and added to the existing data or any database. However, every effort will be made to follow all patients for safety.

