9.1.2 PLX3397

The study treatment PLX3397 HCl is supplied in 200 mg immediate-release capsules for oral administration.

As of Amendment 6, PLX3397 should be administered once a day, and may be taken with food and can be taken with approximately 240 mL (8 oz.) of water. For subjects instructed to take PLX3397 as BID and on an empty stomach before Amendment 6, the dosing regimen should change to QD going forward and it may be taken with food. The dose should be taken at approximately the same times of the day and approximately 24 hours apart for QD dosing. Study drug should be swallowed whole and not crushed, chewed, or dissolved in water. A dosing period of up to 1 hour is permissible if required by the number of tablets to be taken or as convenient for the patient.

For patients receiving both PLX9486 and PLX3397, the medications may be taken together at the same time and may be taken with food. For patients who are taking PLX9486 and PLX3397 with food, the drugs should be taken within approximately 30 minutes of a meal or snack or no later than approximately 1 hour after a meal. If more than 2 hours have elapsed from the scheduled time of dosing, the dose should be considered missed. Missed doses should be skipped and not taken as a double dose at the next dosing time point. Subjects who vomit their dose should be instructed NOT to make up that dose.

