9.1.4 Dosing on PK Sample Collection Days

On PK sample collection days, subjects should be instructed *not* to take their morning dose of PLX9486 and PLX3397 or sunitinib (if applicable) at home before the clinic visit. The time of dosing will be recorded in the clinic. For Part 2b and [REDACTED], the evening dose of PLX3397 will be taken by the subject at home. On non-PK sample collection days, the subject will administer PLX9486 (and PLX3397 or sunitinib if applicable) independently and record dosing information in the study drug administration diary.

For patients in all parts of the study, one PK sample should be collected at the end of study visit for all patients and if feasible up to 4 additional PK samples may be obtained on Days 3, 7, 10, and 14 after the last dose.

9.2 Dose Levels for Parts 1 and 2

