9.2.1.2 Part 2: Extension Cohorts

[REDACTED]

Part 2b. Cohorts of patients will be enrolled using the standard “3+3” design. The PLX9486 dose escalation may follow the pattern established in Part 1, starting at $\leq 50\%$ of the MTD/RP2D established in Part 1. In the absence of Grade ≥ 2 toxicity that is considered “possibly” or “probably” related to the study agent and in conjunction with review of the pharmacokinetic data, dose escalation in Part 2b is planned to occur as indicated in [Table 17](#).

Table 17: PLX9486 and PLX3397 Administration in Part 2b: Initial and Potential Dose-escalation Cohorts

Cohort Number	PLX9486 Dose Level (mg/day) ^a	PLX3397 Dose Level (mg/day)
1	Approximately 50% of Part 1 RP2D	600 (200 mg in AM and 400 mg in PM)
2	Approximately 100% of Part 1 RP2D	600 (200 mg in AM and 400 mg in PM)
3	100% of Part 1 RP2D	400 mg QD (Cycles 1 and 2)
		600 mg QD (Cycle 3 +) ^b
4 +	TBD ^c	TBD ^c

RP2D = recommended phase 2 dose; TBD = to be determined

^a PLX9486 administered once-daily (QD) or for higher total daily doses, as split doses (e.g., twice-daily [BID]).

^b At the discretion of the investigator and in the absence of clinically significant drug-related toxicity ([Section 9.3](#)) during Cycles 1 and 2.

^c Based on a review of the data by the Study Committee.

Dose escalation will continue unless there are DLTs in ≥ 2 of 6 patients in one cohort within the first 28 days of continuous dosing.

[figure not shown]
Further dose escalation and reduction in smaller increments may be undertaken at any time based upon emerging safety, PK, and PD data. Dose adjustments may also include increasing the number of patients at a given dose level as a result of the review of safety and PK data by the Sponsor and investigators. In addition, alternative dosing schedules may be explored, such as continuous dosing followed by a rest period, staggered dosing of the agents, etc., depending on the safety, PK, or PD-generated data, as well as data from other ongoing PLX3397 studies.

If a DLT is observed in one patient at a given cohort, an additional 3 patients will be enrolled into the cohort. If DLT is observed in ≥ 2 of at least 6 patients (i.e., $\geq 33\%$) at a dose level, then a lower dose level of PLX9486 may be introduced to the combination regimen. If no DLT is

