9.3 Definitions of Dose-limiting Toxicity

Dose-limiting toxicities (DLTs) are defined as AEs that occur during Cycle 1, are classified as possibly or probably related to the study drug, and meet one of the following CTCAE v4.03 criteria below. DLTs will be evaluated for each cohort and for each dosing schedule. Toxicities that occur during Cycle 2 or later will be reviewed, and their impact on dose-escalation and dosing frequency will be assessed.

In each cohort, to maximize safety, there will be a 24-hour delay between the first subject enrolled and later subjects enrolled. .

Subjects who are considered in dose-escalation decisions are not allowed dose reductions during the DLT assessment window. Subjects who withdraw from the study prior to completing Cycle 1 for any reason other than a DLT will be replaced. Patient numbers must not be re-used.

A subject who experiences a DLT may remain in the trial and continue receiving study drug at a lower dose if the investigator deems the potential benefit outweighs the risk and that the subject is not eligible for, and/or interested in, an alternative therapy after consultation with the Medical Monitor.

Hematologic Toxicities

- Grade 4 neutropenia lasting >7 days
- Grade ≥ 3 neutropenia with fever
- Grade 4 thrombocytopenia
- Grade ≥ 3 thrombocytopenia lasting more than 7 days or associated with clinically significant bleeding
- Grade 4 anemia

Other Toxicities

- Any \geq Grade 3 (AE or laboratory) toxicity despite adequate supportive care/medical management except for the following:
 - Grade ≥ 3 nausea, vomiting, or diarrhea that resolves to Grade ≤ 2 within 72 hours, with or without medical intervention or prophylaxis because this would not be considered treatment-limiting in an oncology population
 - Grade 3 fatigue that resolves to \leq Grade 2 within 14 days because this would not be considered treatment-limiting in an oncology population
 - Grade ≥ 3 asymptomatic changes in alkaline phosphatase, hypomagnesemia, hyperglycemia, or hypophosphatemia that is felt by the investigator to be clinically insignificant
 - Grade 3 asymptomatic increases in transaminases (AST, ALT) confirmed upon repeat testing which resolves to \leq Grade 2 within <5 days
- Any other Grade ≥ 3 toxicity (except those noted above) for which the Principal Investigator or Sponsor deems further dose escalation inappropriate

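### Section 9.1.2 moves PLX3397 to once daily from Amendment 6, but 9.1.4, 10.3 and the Cohort 1 and 2 rows of Table 17 keep the split schedule, and 12.2 counts converted patients' later events under the split-dose level

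*Protocol*

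**What the plan says.** The passages on the PLX3397 schedule, all in current protocol text:

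- **9.1.2 PLX3397:** "As of Amendment 6, PLX3397 should be administered once a day". For patients who started on BID, "the dosing regimen should change to QD going forward and it may be taken with food". The section does not restate the total daily dose after conversion.
- **9.1.4 Dosing on PK Sample Collection Days:** for Part 2b (and a redacted part), "the evening dose of PLX3397 will be taken by the subject at home". No date or amendment limit is attached.
- **10.3 Treatment Group Assignments:** "The initial dose of PLX3397 will be 600 mg/day administered BID".
- **9.2.1.2, Table 17, Cohorts 1 and 2:** "600 (200 mg in AM and 400 mg in PM"). The synopsis table repeats this. Neither carries a note about Amendment 6.
- **Table 17, Cohort 3:** "400 mg QD (Cycles 1 and 2"), then "600 mg QD (Cycle 3" onward) at the investigator's discretion. Cohort 4+ is to be determined.

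The analysis rules that bear on this are:

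- **9.3:** "DLTs will be evaluated for each cohort and for each dosing schedule", with DLTs counted in Cycle 1 only.
- **9.4:** toxicities outside the DLT window are considered when the RP2D is determined.
- **12.2:** safety is summarised by dose level, using the dose originally assigned.

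**The concern.** Two things are at stake.

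The first is operational. The synopsis says that patients are still being treated in Part 2b at the time of this amendment (Amendment 7). On a PK day, a site that follows 9.1.4 directs a second PLX3397 dose that 9.1.2 does not provide for. Anyone entering Cohort 1 or 2 after Amendment 6 would meet a split schedule in Table 17 and a once-daily schedule in 9.1.2.

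The second is analytic. Section 9.1.2 creates patients whose treatment has a split-dose period followed by a once-daily period. Grouping by originally assigned dose places both periods under the split-dose level. Part 2b exists to establish an RP2D for the combination, and 9.4 lets later toxicity count towards it. Section 7.1 also allows Part 1 patients who progress to roll over to the combination at the current dose or the RP2D, so it matters which schedule the supporting data describe.

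**Working it through.** **1. The schedule passages side by side**

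| Place | PLX3397 schedule | Limited to before Amendment 6? |
|---|---|---|
| 9.1.2 | once daily; earlier BID patients converted | states the change itself |
| 9.1.4 | evening dose on PK days, Part 2b | no |
| 10.3 | 600 mg/day BID, as the initial dose | no |
| Table 17 and synopsis, Cohorts 1 and 2 | 200 mg AM + 400 mg PM | no |
| Table 17 and synopsis, Cohort 3 | 400 mg once daily, then 600 mg once daily from Cycle 3 | not needed; agrees with 9.1.2 |

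Section 9.1.4 is the clearest conflict, because it is an undated instruction for conduct. The Cohort 1 and 2 rows and 10.3 may describe what was done before the change, but nothing in them says so.

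**2. The plan's own DLT figures**

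Table 29 gives the probability of escalating in Part 2b. With one true DLT rate p in the cohort, the 3+3 formula is (1−p)³ + 3p(1−p)²·(1−p)³. For p = 10% to 70% this gives 0.906, 0.709, 0.494, 0.309, 0.172, 0.082 and 0.032. The table's 0.91, 0.71, 0.49, 0.31, 0.17, 0.08 and 0.03 are reproduced.

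**3. Do the reported DLT data mix schedules?**

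The DLT window is 28 days (9.2.2). Section 5.5.1.2 reports 11 patients, all on 600 mg as a split dose, with no DLTs. (The rows of Table 12 sum to 4 + 8 = 12; the text says 11.) The one-sided 95% upper limit for 0/11 is 1 − 0.05^(1/11) = 23.8%; for 0/12 it is 1 − 0.05^(1/12) = 22.1%. Either figure describes the split dose only. The reported data show no mixing.

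Mixing could arise only if patients enrolled in Cohort 1 or 2 after Amendment 6 took PLX3397 once daily and were pooled with the earlier ones. For illustration, assume (these rates are not in the protocol) that the first three patients have DLT rate p1 on one schedule and the next three have p2 on the other. Escalation then has probability (1−p1)³ + 3p1(1−p1)²·(1−p2)³:

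- p1 = 20%, p2 = 40%: 0.512 + 0.384 × 0.216 = 0.595, against 0.709 and 0.309 for each schedule alone.
- p1 = 10%, p2 = 30%: 0.729 + 0.243 × 0.343 = 0.812, against 0.906 and 0.494.

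This shows what pooling could do. It is not evidence that pooling occurred, and 9.3 already asks for DLTs by schedule.

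**4. Which cohort has 600 mg once daily in its DLT window?**

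Cohorts 1 and 2 list 600 mg split. Cohort 3 lists 400 mg once daily in Cycles 1 and 2 and reaches 600 mg once daily only from Cycle 3, after the window. Cohort 4+ is undefined. So no numbered cohort does. If a converted patient's daily total stays at 600 mg (an assumption, since 9.1.2 does not restate it), the largest single dose goes from 400 to 600 mg, a ratio of 600/400 = 1.5.

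**5. What happens after Cycle 1**

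A Cohort 1 patient converted under 9.1.2 keeps the original assignment. Under 12.2, events after conversion are therefore tabulated with the split-dose level, and 9.4 allows them to inform the RP2D.

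PK is affected too. The Table 3 footnotes call for predose samples on Day 1 of Cycle 3 onward. Under 9.1.2 such a sample follows the previous PLX3397 dose by about 24 hours; under the split schedule it follows a dose taken the evening before.

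Food can change at the same time, because 9.1.2 also permits dosing with food. Steady-state PLX3397 AUC0-24 in Table 13 is 64,000 fasted (N = 4) and 112,000 fed (N = 7), a ratio of 112,000/64,000 = 1.75. For patients who began fasted, schedule and food condition may therefore shift together.

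**The case against.** The strongest reply is that this is a dated change, not a contradiction. Section 9.1.2 names Amendment 6 as the point of change, 10.3 speaks only of the initial dose, and the split rows of Table 17 match what the reported patients received. That is a fair reading of 10.3 and a possible one of the table rows, where the defect may be only a missing label. It does not excuse 9.1.4, which is an undated instruction for PK days.

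A second reply is that per-schedule DLT evaluation is already required by 9.3, and that splitting patient time by schedule is normal SAP detail. The first half stands. The second half would stand if the protocol were silent, but 12.2 states a grouping rule, and that rule produces the misfiling.

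Three stronger readings are tempting, and the document does not support them:

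- A reader might infer that the DLT evaluation of 600 mg/day already mixes two schedules. All 11 reported patients took the split dose, and Cohort 3 is on 400 mg once daily during its window.
- A reader might infer that Table 13 reports PLX3397 exposure over 12 hours only. Its footnote applies AUC0-12 to the Day 1 column; the steady-state column is AUC0-24.
- A reader might infer that the RP2D cannot be tied to a schedule at all. Table 17 defines each numbered level together with its schedule. What is blurred is the later-cycle evidence under the split levels.

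**Conclusion.** This is an internal inconsistency left by incomplete amendment editing. Section 9.1.4 conflicts with 9.1.2 as written, and 10.3, the Cohort 1 and 2 rows of Table 17 and the synopsis table lack a limit to the period before Amendment 6. The analytic consequence is confined to data after Cycle 1: by 12.2, once-daily events of converted patients are counted at the split-dose level, while 9.4 lets them bear on the RP2D.

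The size cannot be fixed from the protocol. Of the 11 reported patients, between 0 and 11 could have been converted, depending on how many were still on PLX3397 at Amendment 6. The 1.5-fold change in largest single dose assumes an unchanged 600 mg daily total. The reported DLT result is unaffected, but it says nothing directly about 600 mg once daily. The point should be corrected; it does not invalidate the Part 2b design.

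**What to change.** - Reconcile 9.1.4, 10.3, the Cohort 1 and 2 rows of Table 17 and the synopsis table with 9.1.2, with an explicit date or amendment limit wherever a passage describes an earlier regimen. Which schedule is right is for the sponsor and investigators; this review takes no view.
- In 12.2, keep the summary by originally assigned dose if wanted, and add a presentation of Part 2b later-cycle safety and PLX3397 PK by schedule actually taken (split or once daily). Assign a switched patient's time, events and samples to the schedule in force at that moment.
- State the number of patients converted and the cycle of conversion.

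The cost is four text corrections, one added sentence in 12.2 and one derived variable. Dosing is already recorded in patient diaries and, on PK days, in the clinic (9.1.4, 10.5), so no new data collection is needed.
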